- Caffeine + AIH. Following baseline testing, subjects will consume 3 mg/kg of caffeine. Caffeine capsules will be prepared for each subject based upon the weight recorded at the screening visit. AIH will then commence in the same pattern as described above beginning 1 hour after caffeine consumption.

## Aim 1 Dependent Variables – Maximal Voluntary Contractions

- Maximal respiratory pressures maximal voluntary static contractions of the inspiratory or expiratory muscles against a closed valve, measured at the mouth (64). Sniff nasal inspiratory pressure measures inspiratory force generation at the nose. This more natural maneuver has lower variability and learning effects (65) and appears to decline in conjunction with the need for nocturnal ventilation in ALS (66, 67). The test will be repeated until 3 measurements are obtained within 10% variability; a minimum 20-second rest will be provided between measurements. Maximal inspiratory pressures will be measured at baseline and 60 min post-AIH.
- Peak cough flow the maximal expiratory airflow measured through a facemask during a maximal-effort voluntary cough. Subjects will repeat 3-5 voluntary coughs to achieve 3 measurements within 10% variability. The peak cough flow will be measured at baseline and 30 min post- intervention.
- Maximal voluntary grip force maximal static voluntary handgrip contractions will be evaluated in a seated position with the arm at the side and elbow flexed to 90 degrees. The test will be repeated until 3 measurements are obtained with <10% variability, and a minimum 15-second rest between measurements. Significant gains in isometric force have been reported with a single AIH session in patients with spinal cord injury. Grip strength will be measured at baseline, 30 and 60 minutes post-intervention.

# Aim 2 Dependent Variables – Resting/automatic respiratory motor function

- Minute ventilation the pneumotachograph and pressure transducer connected to the face mask will record breath-by-breath flow, volume, mouth pressure, and breathing rate. After achieving a stable tidal volume, 5 minutes of tidal breathing will be recorded. Tidal breathing will be measured at baseline, during hypoxic episodes, immediately following AIH, and at 30 and 60 minutes post-intervention.
- Ventilatory drive. Respiratory drive will be estimated with pressure generation against a transiently occluded airway in the first 0.1 sec of inspiration (ie. P0.1); subjects will

be seated upright and breathing quietly through the face mask. An inspiratory valve will be manually occluded during the expiratory phase of a breath and will be maintained until the end of the subsequent inspiratory effort. Five measurements will be conducted, with 5-15 un-occluded breaths between each  $P_{0.1}$  measurement. This validated test is resistant to learning or sensory bias and reflects unaltered neuromuscular effort (68, 69).  $P_{0.1}$  will be measured at baseline, 30 and 60 minutes post-intervention.

Respiratory muscle EMG. Surface EMGs of the respiratory muscles (up to six muscles, bilaterally: scalene, sternocleidomastoid, 2nd parasternal, 5th external intercostal, 8th external intercostal, and diaphragm) will be recorded during the test session. The root mean square (RMS) of each muscle will be averaged. Multi-muscle activation will be calculated using a validated, vector-based analysis(70) that provides a magnitude (Response Vector) and pattern (Similarity Index) of composite EMG activity. We will then compare multi-muscle activity from each ALS subject to the Prototype Response Vector calculated as the average Response Vector and Similarity Index calculated from the pooled control subjects (71).

Aim 3 Dependent Variables

- Maximal respiratory pressures as described in Aim 1
- Maximal voluntary handgrip force as described in Aim 1
- Tidal breathing pattern as described in Aim 2
- Markers of caffeine metabolism and adenosine-mediated AIH. Saliva specimens will be collected at the screening visit and processed for single nucleotide polymorphisms in three specific genes. Polymorphisms in CYP1A2 (rs762551), ADORA2A (rs5751876), and BDNF (rs6265) will be tested using a commercially available TaqMan assay with PCR instrument and genotyping analysis software.
- Salivary caffeine Saliva specimens will be collected before baseline testing and 60 minutes post-AIH, to measure changes in salivary caffeine levels. Salivary caffeine will be analyzed using a HPLC assay. The caffeine powder used by Westlab Pharmacy will be available to UF's ICBR to create a caffeine standard for assay analysis.

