## Eligibility Criteria.

Subjects will be eligible to participate if they have a clinical diagnosis of ALS or are a healthy adult; are between 21 and 75 years of age; and have a baseline FVC >60% predicted for age, sex and height. Baseline FVC is routinely performed at every clinic for ALS patients. The AIH study team (PI or coordinator) will email a PFT report request to the clinic respiratory therapist, in advance of clinic. On the day of clinic, the respiratory therapist will upload the requested PFT reports directly into EPIC. After clinic, the AIH study coordinator will locate the PFT report in EPIC and save it to the electronic study binder. If the PFT report indicates the FVC is within study criteria, the subject can be contacted for an appointment. If the FVC falls below study eligibility, the patient will not be scheduled for a screening visit.

Patients will be classified into two groups: 1) uses no form of external respiratory support (IND); and 2) and uses non-invasive external respiratory support while sleeping for at least 2 nights per week to assist night time breathing or treat sleep apnea (NIV). Since 4-6 subjects in each group may fail to meet all eligibility criteria or attend the second testing session, we request to enroll up to 18 patients with ALS, with the goal of completing all study procedures in 12 patients. In addition, we request enrollment of up to 30 healthy controls to complete all study procedures in 20 (up to 20 healthy controls may be needed as a reference set for the EMG data analysis described on *page 10*). The healthy controls will be recruited via listings for this study on CT.gov and the StudyConnect website.

Patient and control participants are ineligible if they: are pregnant, have diagnosed cardiovascular disease, have a BMI >35 kg/m^2, currently take selective serotonin reuptake inhibitors (SSRI), have a history of seizures, have a history of hospitalization for sepsis, had a respiratory infection or took antibiotic medications within the past 4 weeks, use external respiratory support during any waking hours, participate in a pharmaceutical trial to treat ALS, or have any other medical condition the PI ([name]) or medical director ([name]) identify would make it unsuitable to participate.

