### **Statistical Analysis**

The outcomes for both aims are largely quantitative and continuous. Sample distributions and summary statistics will be calculated for each outcome, and non-linear data distributions will be transformed as needed. Study outcomes for Aims 1-2 include acute changes in voluntary strength, resting ventilation, and respiratory drive. Each of these will be evaluated with 3-way repeated measures ANOVAs. Factors will be subject group (patient vs control), AIH condition (AIH vs Sham AIH), and time (pre, 0 minutes post, 30 minutes post, 60 minutes post); Tukey's post hoc test will be used to assess individual differences. A separate ANOVA will compare the independent effect of caffeine on motor function 60 minutes post-AIH. We will work with BERD to use genetic testing results to model independent effects of caffeine metabolism genotype on AIH motor facilitation, as pilot data to estimate sample size for a larger, future project. For the analysis of sEMG Response Vector and Similarity Index, baseline FVC will be used as a covariate. These will be tested with 2-way repeated measures ANOVAs (AIH only, factors: subject group

and time). Relationships between variables will be evaluated with Pearson's correlation. Statistical significance will be p<0.05.

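### As the plan reads, each control's EMG Similarity Index is scored against a prototype containing that control, which biases the patient-versus-control comparison

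*Combined protocol and SAP*

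**What the plan says.** Three places bear on this.

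- **Aim 2 Dependent Variables, respiratory muscle EMG.** The reference is a "Prototype Response Vector calculated as the average Response Vector and Similarity Index calculated from the pooled control subjects". Only ALS subjects are named as being compared with this prototype; the sentence opens "We will then compare multi-muscle activity from each ALS subject to the".
- **Statistical Analysis.** The covariate is set out first: "For the analysis of sEMG Response Vector and Similarity Index, baseline FVC will be used as a covariate". The test is given next: "These will be tested with 2-way repeated measures ANOVAs (AIH only, factors: subject group"; the second factor is time. For the three-way ANOVAs in the same section, group is defined as patient versus control: "Factors will be subject group (patient vs control), AIH condition (AIH vs Sham AIH), and time".
- **Eligibility Criteria.** "we request enrollment of up to 30 healthy controls to complete all study procedures in 20", with the explanation that "up to 20 healthy controls may be needed as a reference set for the EMG data analysis". The goal for ALS is 12 completers out of up to 18 enrolled.

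None of these sections describes a leave-one-out step, a split of the controls or an outside reference cohort. None says at which time point the prototype is formed.

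**The concern.** A group test on the Similarity Index cannot be run unless controls have an index as well. The largest reference set the plan mentions, 20, is also its whole target of completing controls, so no other controls are set aside for scoring. Read together, the sections lead to each control being measured against an average to which it contributed one part in 20, while patients contribute nothing. A subject is always pulled towards an average that contains it, so the control group would appear more typical than the patient group even if the two populations were identical.

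The Abstract's exploratory hypothesis for Aim 2 has two parts: that ALS patients recruit respiratory muscles differently from healthy people, and that AIH partly corrects this. The artefact pushes the first part towards a positive answer. Aim 2 is exploratory, but the Eligibility Criteria section says the main purpose of the study is pilot data for a larger grant. A spurious group difference could be carried into that application.

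**Working it through.** The plan gives no effect size, SD or error rate for the EMG comparison, so there is no figure to reproduce.

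**Inputs from the documents:** 20 completing controls, 12 completing patients, up to six muscles recorded bilaterally (so 6 or 12 channels), significance at 0.05 (sidedness not stated; two-sided taken).

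**Assumptions not in the documents:** index = cosine between a subject's vector and the control mean; log-normal RMS amplitudes with equal muscle means; between-subject CV 0.3 to 1.0; identical ALS and control distributions.

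**1. Direction, without simulation.** For n independent control vectors with total variance σ², the expected squared distance to the control mean is:
- control inside the mean: σ²(1 − 1/n)
- patient outside it: σ²(1 + 1/n)
- ratio: (n − 1)/(n + 1) = 19/21 = 0.905 for n = 20

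Controls are expected to lie closer with no true difference. With leave-one-out, a control's value is σ²(1 + 1/19) = 1.053σ² against 1.050σ² for a patient, a ratio of 400/399 = 1.0025, so the imbalance all but vanishes.

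**2. Size at one time point, simulated under no difference (20 vs 12, 6,000 runs per setting, plain t-test).**
- Control index minus ALS index: 0.004 to 0.027, or 0.18 to 0.33 SD.
- Rejection: 8.6% to 15.2%. The part pointing to controls being more typical is 7.8% to 14.8%; the opposite direction is 0.4% to 0.9%.
- A further simulation on the same lines gave 0.18 to 0.35 SD and 8% to 17%.
- Leave-one-out: −0.012 to +0.002 SD, rejection 4.9% to 5.7%.

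**3. Adding the planned FVC covariate.** With FVC assumed 20 points lower in ALS, SD 12, and unrelated to the index, simulated rejection was 7% to 12%. A hand check agrees:
- SE of a standardised difference: √(1/20 + 1/12) = 0.365.
- Bias over SE: 0.18/0.365 = 0.49 to 0.35/0.365 = 0.96. By normal approximation, rejection is about 8% to 16%.
- Variance of FVC due to group: (20/32)(12/32)(20²) = 93.75; within group 12² = 144; R² = 93.75/237.75 = 0.394.
- The SE of the group effect grows by √(1/(1 − 0.394)) = 1.28. Bias over SE falls to 0.38 to 0.75, and rejection to about 7% to 12%.

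**4. Four time points (6 channels, 3,000 runs per setting, no FVC covariate).**

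| Quantity | Result |
|---|---|
| Group main effect, baseline prototype | 7.6% to 10.4% |
| Group main effect, prototype re-formed at each time | 9.7% to 19.6% |
| Group main effect, leave-one-out | 4.7% to 6.5% |
| Group-by-time contrast, self-included | 5.0% to 7.5% |
| Control index change after baseline, baseline prototype | fall of 0.001 to 0.012 |
| ALS index change after baseline, baseline prototype | about 0 |

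**The case against.** The strongest reply is that the premise is inferred. The EMG section speaks only of ALS subjects being compared with the prototype, and it cites published methods papers that may say how reference subjects are scored. That stands as a limit: a reader might infer that the plan states outright that controls are scored against themselves, and it does not. But the group factor requires a control index, and the plan offers no other way of obtaining one.

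The rates are also not those of the planned model. The index formula, any normalisation of RMS and the timing of the prototype are not given, and most of the simulations leave out FVC. This stands too. Adjustment reduces the excess rejection but leaves the bias in place. The direction is firm; the size is conditional.

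A reader might further infer that the artefact manufactures the treatment effect, since a baseline prototype makes control similarity drop slightly afterwards and so makes patients seem to move towards normal. The calculations do not support that as a material problem. Group-by-time rejection stays close to nominal, and change within ALS patients is not biased by self-inclusion because no patient is in the prototype. The Specific Aims section frames the EMG question as whether AIH restores more normal recruitment, and that question is largely untouched.

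Nor does the point reach every EMG outcome. A Response Vector magnitude that is not scored against the prototype is unaffected. Larger distortions with, say, 10 controls can be computed, but 10 is not the planned number.

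**Conclusion.** The concern holds for one test: the patient-versus-control main effect on the Similarity Index. On the only scoring the text supports, that effect is biased towards finding ALS recruitment patterns different. At 20 versus 12 the inflation is about 0.2 to 0.35 SD. The nominal 5% test rejects about 8 to 17% of the time at one time point without FVC, and about 7 to 12% with FVC assumed 20 points lower in ALS and unrelated to the index. These sizes rest on a cosine index and log-normal amplitudes, and they shift with the CV, the channel count and the timing of the prototype; re-forming it at each time point took the upper end to 19.6%. Because the outcome is exploratory, this is a correction that should be made rather than a threat to the study.

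**What to change.** In the EMG paragraph of the Aim 2 dependent variables, state that:

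1. each control's Similarity Index is calculated against a prototype formed from the other controls only;
2. that control's prototype is held fixed across all time points;
3. the time point at which prototypes are formed is named;
4. each ALS patient is scored against the full control prototype.

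Use these values in the two-way ANOVA in the Statistical Analysis section. If the sponsor already intends a different way of scoring controls, the same place should say so. The cost is a sentence or two and a few lines of code, with no new data or visits.

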### **Statistical Analysis**

The outcomes for both aims are largely quantitative and continuous. Sample distributions and summary statistics will be calculated for each outcome, and non-linear data distributions will be transformed as needed. Study outcomes for Aims 1-2 include acute changes in voluntary strength, resting ventilation, and respiratory drive. Each of these will be evaluated with 3-way repeated measures ANOVAs. Factors will be subject group (patient vs control), AIH condition (AIH vs Sham AIH), and time (pre, 0 minutes post, 30 minutes post, 60 minutes post); Tukey's post hoc test will be used to assess individual differences. A separate ANOVA will compare the independent effect of caffeine on motor function 60 minutes post-AIH. We will work with BERD to use genetic testing results to model independent effects of caffeine metabolism genotype on AIH motor facilitation, as pilot data to estimate sample size for a larger, future project. For the analysis of sEMG Response Vector and Similarity Index, baseline FVC will be used as a covariate. These will be tested with 2-way repeated measures ANOVAs (AIH only, factors: subject group

and time). Relationships between variables will be evaluated with Pearson's correlation. Statistical significance will be p<0.05.

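### The repeated-measures ANOVAs have no missing-data method, although some subjects are expected to miss session 2; a linear mixed model would use incomplete records without extra patients

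*Combined protocol and SAP*

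**What the plan says.** Under Statistical Analysis, changes in voluntary strength, resting ventilation and respiratory drive are handled alike: "Each of these will be evaluated with 3-way repeated measures ANOVAs". The factors are subject group, AIH condition and "time (pre, 0 minutes post, 30 minutes post, 60 minutes post"). The threshold is given as "Statistical significance will be p<0.05". The EMG indices get 2-way repeated-measures ANOVAs. Nothing is said about missing data, the analysis set, the covariance structure or a degrees-of-freedom correction.

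Eligibility Criteria anticipates losses: "Since 4-6 subjects in each group may fail to meet all eligibility criteria or attend the second testing session". It answers them by over-enrolment. For ALS, "we request to enroll up to 18 patients with ALS, with the goal of completing all study procedures in 12 patients"; for controls, "we request enrollment of up to 30 healthy controls to complete all study procedures in 20". It does not separate screen failures from subjects who attend one session only, and it does not say what happens to the latter's data.

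For maximal respiratory pressures, the Aim 1 Dependent Variables section says: "The test will be repeated until 3 measurements are obtained within 10% variability". Grip has a similar rule. Neither says what is recorded if agreement is never reached.

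**The concern.** A group by condition by time ANOVA in its classical form needs every condition-by-time cell from every subject. One missed session, or one missing reading in an attended session, removes the whole subject from that outcome's analysis.

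The documents give reasons to expect gaps. Subjects may stop at any time, AIH is ended on heart-rate, blood-pressure or saturation limits, and fatigue is said to reduce test performance. With 12 ALS completers as the goal, each lost subject costs precision. If loss follows a poor earlier response, dropping those subjects can also bias the AIH-sham comparison. A method that uses partial records is available and changes only the analysis text.

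**Working it through.** **The plan's own figures.** For ALS, 18 - 6 = 12, so the completer goal follows from the upper end of 4-6 if the ALS group is meant. For controls, 30 - 20 = 10, whereas a loss of 4-6 would need only 24 to 26 enrolled. Because screen failures are pooled with session-2 losses, the ALS patients with exactly one session of data number anywhere from 0 to 6.

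**Step 1: complete cases among 12 patients who attend both sessions.** The number of cells is k = scheduled time points x 2 sessions. Expected complete cases are 12(1 - p)^k, where p is the chance that a reading is missing. The documents give no p; 1%, 2% and 5% are assumed, with independence between readings.

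| Outcome | k | p = 1% | p = 2% | p = 5% |
|---|---|---|---|---|
| MIP (baseline, 60 min) | 4 | 11.5 | 11.1 | 9.8 |
| Grip (baseline, 30, 60 min) | 6 | 11.3 | 10.6 | 8.8 |
| Tidal breathing (baseline, 0, 30, 60 min) | 8 | 11.1 | 10.2 | 8.0 |

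For example, grip at 5% is 12 x 0.95^6 = 12 x 0.735 = 8.8.

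**Step 2: variance of the AIH-minus-sham 60-minute change in grip.**
- Complete cases: the variance is proportional to 1/N, with N binomial(12, (1 - p)^6). The inflation, E(12/N) - 1, is about 7%, 14% and 40%. The simple ratio at 5%, 1/0.735 = 1.36, is lower because the mean of 1/N exceeds 1 over the mean of N.
- Mixed model: generalised least squares on all available cells, averaged over random missing patterns, with variances treated as known (for example subject 1, session 0.1, residual 0.1; assumed). The inflation is about 1 to 2%, 3% and 7 to 8%. Other variance ratios gave nearly the same values.

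**Step 3: one-session patients.** Take n = 12 complete pairs, m one-session patients split evenly between AIH and sham, and between-session correlation rho of the change score (not given in the documents). In units of 1/variance of a change score, the pairs carry n/(2(1 - rho)) and the one-session patients m/4. The relative gain is m(1 - rho)/(2n).
- m = 6: 0.25(1 - rho), which is 25%, 17.5%, 12.5%, 7.5% and 2.5% at rho = 0, 0.3, 0.5, 0.7 and 0.9. This equals 15.0, 14.1, 13.5, 12.9 and 12.3 complete pairs.
- m = 2: 8.3% at rho = 0, falling to 0.8% at rho = 0.9.
- m = 0 (all losses are screen failures): 0.

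**Step 4: simulation of one-session loss.** There were 3000 runs, with 18 ALS patients starting and an assumed effect of 0.8 SD where power or bias is quoted.
- No missing data: power was identical for the complete-case test and the mixed model (0.890 with 18 pairs, 0.722 with 12, at rho 0.5).
- Six lost at random: 0.584 against 0.651 at rho 0.3, 0.716 against 0.760 at 0.5, and 0.980 against 0.983 at 0.8 (complete-case first).
- Loss dependent on a poor session-1 response: complete-case bias was -0.048, -0.033 and -0.013 SD at rho 0.3, 0.5 and 0.8. Mixed-model bias was at most 0.007 SD.
- Type I error of the mixed model with six lost: 4.4 to 5.2% with a t reference on pairs minus 1 degrees of freedom, but 6.9 to 8.2% with a plain Wald z test. Kenward-Roger itself was not simulated.

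**The case against.** The strongest reply is that 12 and 20 are already completer targets after over-enrolment, so the planned analysis number is not reduced, and that a pilot sized by time and budget has no power claim to undermine. The first part stands for session-2 losses: step 3 is a modest gain, possibly zero. It does not settle single missing readings, because attending both sessions does not guarantee every reading. The second part limits the seriousness but is no reason to discard data already collected.

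Several stronger readings are tempting and are not supported:
- **That the trial will fall from 12 patients to 8 or 9.** This needs the assumed 5% rate, independence, and the 6- or 8-cell outcomes. If gaps cluster in a few weak patients, fewer subjects are lost. MIP has only four cells.
- **That the 10% agreement rule creates missing values.** The text says to keep repeating. It does not say that efforts failing to agree are set to missing, and the rule does not apply to quiet tidal breathing.
- **That the plan prescribes listwise deletion.** It does not say so. Deletion is how the named method is usually run.
- **That sphericity is a general problem.** With two time levels, as for MIP, it cannot be violated. Grip and P0.1 have three levels and only tidal breathing has four. Any figure for the inflation depends on an assumed covariance.
- **That a mixed model is free or cures all bias.** If a patient cannot produce an effort, missingness may depend on the unobserved value, and the mixed model does not remove that bias.

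**Conclusion.** The point holds as a gap in the analysis plan with an inexpensive remedy; it does not invalidate the design. The plan expects incomplete records, names a method that ordinarily discards them, and states no alternative.

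The main gain is for single missing readings. Even at an assumed 2%, complete-case variance for grip rises about 14%, against about 3% with a mixed model. The gain from one-session patients is smaller and depends on two unknowns: how many of the six expected ALS losses have outcome data, and the between-session correlation. The demonstrated bias is small, at most 0.048 SD under one assumed mechanism. All sizes rest on assumed missing rates, independence and variance components, since the documents give none.

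**What to change.** Replace the ANOVA wording with a linear mixed model for each outcome:
- fixed effects for group, condition, time, their interactions, and period;
- random effects for subject and for session within subject;
- Kenward-Roger degrees of freedom, not plain Wald tests;
- only the time points at which that outcome is measured: two for MIP, three for grip and P0.1, four for tidal breathing;
- every subject with at least one session of outcome data;
- the AIH-versus-sham change in ALS tested as a model contrast.

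Report one-session subjects separately from screen failures, and state the missing-at-random assumption together with the reasons for missing readings.

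The cost is revised analysis text and somewhat more analysis work. No patients, visits or measurements are added. The price is reliance on missing at random, which may fail when weakness prevents an effort, and on the small-sample correction.

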### Preliminary studies in rodent models of ALS:

Diminished breathing ability can be partially restored by harnessing the intrinsic capacity for plasticity (1). In rats with incomplete cervical spinal injury, even a single presentation of AIH increases phrenic/diaphragm function ipsilateral to injury (22, 49). Repetitive AIH for one week enhances both the magnitude and duration of this effect (20, 31, 35). The mechanism of functional recovery is a shifting function of time post-injury; for example, 1 week of daily AIH beginning 1 week post-injury improves breathing capacity by an adenosine dependent, serotonin-independent mechanism (31, 50). On the other hand, 1 week of daily AIH elicits functional improvement of breathing capacity by a serotonin-dependent, adenosine constrained mechanism. Thus, multiple, time-dependent mechanisms can contribute to the functional plasticity observed. Both mechanisms of functional recovery are transient, although prolonged repetitive AIH exposures appear to elicit more robust and prolonged functional recovery. We are currently exploring optimal protocols with respect to both the amplitude and duration of functional improvement.

Preliminary studies demonstrate that even a single AIH exposure restores diminished phrenic nerve activity during late-stage disease in a rat model of ALS, the SOD1G93A transgenic rat (10, 11, 51, 52). Indeed, in end-stage rats, AIH-induced phrenic motor facilitation is nearly double that found in wild-type littermates or in mutant rats during early stage disease (52). In end-stage ALS rats, enhanced AIH-induced phrenic motor facilitation utilizes the same serotonin-dependent mechanisms as in wild-type rats (10). These preliminary data and proof of concept studies in humans with incomplete spinal cord injury provide a strong rationale to evaluate responses to a single session of AIH in patients with ALS. Our initial investigations on a single AIH presentation will guide efforts as we work to evaluate repetitive AIH as a potential therapeutic modality in humans with ALS.

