## Specific Aims

**Aim 1: Test the hypothesis that a single AIH trial increases maximal respiratory and non-respiratory motor function in ALS.** Dependent variables will include: maximal inspiratory pressure (MIP) and maximal handgrip force (MHGF). We will address the following questions:

- a. Does AIH increase voluntary inspiratory pressure generation?
- b. Does AIH increase maximal handgrip force?
- c. Are baseline MIP and MHGF inversely related to AIH-induced facilitation?

Aim 2: Test the hypothesis that a single AIH trial increases resting respiratory motor function in ALS. Dependent variables will include: resting tidal volume, respiratory EMG at rest, resting ventilatory drive. Three questions will be addressed:

- a. Does AIH increase resting tidal volume?
- b. Does AIH increase the resting ventilatory drive?
- c. Does AIH increase respiratory muscle activation and restore more normal respiratory muscle recruitment patterns?

Aim 3: Test the hypothesis that pre-treatment with caffeine will augment respiratory and non-respiratory motor function. Dependent variables will include: maximal respiratory pressures, maximal grip force, resting tidal volume, EMG. Three questions will be addressed:

- a. Does acute consumption of caffeine enhance AIH-induced facilitation of respiratory and non-respiratory motor function?
- b. Is there a difference in AIH-induced facilitation of respiratory and nonrespiratory motor function between slow and fast caffeine metabolizers?
- c. Does acute consumption of caffeine improve the AIH-induced increase in respiratory muscle activation?

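### The Statistical Analysis section names no test for Aim 1; a within-ALS AIH-versus-sham contrast, adjusted for session baseline, should be named for MIP and handgrip force

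*Combined protocol and SAP*

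**What the plan says.** Specific Aims states Aim 1 as "Test the hypothesis that a single AIH trial increases maximal respiratory and non-respiratory motor function in ALS", with MIP and MHGF as dependent variables. Its first two questions are "Does AIH increase voluntary inspiratory pressure generation" and "Does AIH increase maximal handgrip force". Each subject has one AIH and one sham session, in random order.

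The Statistical Analysis section says: "Study outcomes for Aims 1-2 include acute changes in voluntary strength, resting ventilation, and respiratory drive". Each outcome goes into a three-way repeated-measures ANOVA. The factors are subject group (patient or control), "AIH condition (AIH vs Sham AIH), and time (pre, 0 minutes post, 30 minutes post, 60 minutes post". The only follow-up is: "Tukey's post hoc test will be used to assess individual differences". Significance is p<0.05, with no sidedness given. No main effect, interaction, time point or contrast is tied to Aim 1. The text speaks of changes yet lists the pre-intervention value as a time level, so it is unclear whether raw values or changes are modelled.

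The measurement schedule is in the two Dependent Variables sections for Aims 1 and 2. MIP is taken at baseline and 60 minutes, cough flow at baseline and 30, and grip and P0.1 at baseline, 30 and 60. Tidal breathing has all four analysis times.

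**The concern.** The sham crossover makes AIH versus sham within ALS patients the natural reading of Aim 1. The model contains the data for that comparison, but its omnibus terms target something else:

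- **Condition × time** estimates the AIH effect averaged over patients and controls.
- **Group × condition × time** asks whether patients and controls respond differently. The Abstract declares this interest, but it is a separate question from Aim 1.
- **Tukey** can reach the ALS pair, but only as one of several. If raw values are modelled, a 60-minute AIH-versus-sham pair takes no account of each session's own baseline.

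The study seeks proof of concept in ALS. If the Aim 1 test is chosen after the data are seen, the same data can support different conclusions.

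The protocol's rationale gives reason to consider controls who also respond. In end-stage ALS rats it reports that "AIH-induced phrenic motor facilitation is nearly double that found in wild-type littermates or in mutant rats during early stage disease". Patients here must "have a baseline FVC >60% predicted for age, sex and height", so they need not resemble end-stage animals. Carrying rat phrenic activity over to human MIP and grip is an extrapolation. I therefore treat control responses of zero, half and equal size as planning cases, not predictions.

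**Working it through.** The plan states no power, SD or effect size, so there is no figure to reproduce. I compared the candidate tests on common assumptions.

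**Inputs.** Completers are 12 ALS and 20 controls (Eligibility Criteria). Alpha is 0.05, taken as two-sided. Assumed: d, the AIH-minus-sham difference in change from baseline divided by its SD, with equal SD in both groups. The outcome has two time levels (MIP: pre and 60), so each term has 1 df. Power comes from the noncentral t distribution.

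**Formulas.** Let s = √(1/12 + 1/20) = 0.365.

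- Three-way term: ncp = (d_ALS − d_ctrl)/s, df 30.
- Condition × time, groups weighted equally: ncp = [(d_ALS + d_ctrl)/2]/(s/2), df 30.
- Named within-ALS contrast, ALS-only error: ncp = d_ALS × √12, df 11.
- Tukey pair on changes (4 cells, 6 pairs): same ncp, df 30, critical value q(0.95; 4, 30)/√2 = 2.72.

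At d_ALS = 0.9 and no control response, the three-way ncp is 0.9/0.365 = 2.46. The ncp of the named contrast is 0.9 × 3.464 = 3.12.

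**Power, with controls responding zero / half / equally**

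| d_ALS | Three-way | Tukey pair on changes | Named ALS contrast |
|---|---|---|---|
| 0.7 | 46% / 15% / 5% | 40% | 60% |
| 0.9 | 66% / 22% / 5% | 65% | 81% |
| 1.1 | 83% / 31% / 5% | 85% | 93% |

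The last two columns do not depend on the control response. At d_ALS = 0.9, condition × time has 66% / 95% / 99.7%, but for the two-group average.

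**Only controls respond (d_ALS = 0).** At d_ctrl = 0.5/0.8/1.0, condition × time and the three-way term are each significant in about 26%/56%/75% of trials, but often not in the same trials. In 200,000 simulated trials per case, condition × time was significant while the three-way term was not in about 21%/27%/20%. A reader who checks both terms can still credit ALS with an effect that only controls have.

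**Form of the baseline adjustment (n = 12, 40,000 simulated trials per case).** The true effect is 1.8 residual SD. A difference in change combines four independent residuals, so its SD is 2 residual SD and d = 1.8/2 = 0.9. Session SD is the variation shared by the pre and post values of one session.

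| Session SD ÷ residual SD | Difference in change | Baseline difference as covariate |
|---|---|---|
| 0 | 81% | 96% |
| 0.5 | 81% | 93% |
| 1 | 81% | 87% |
| 2 | 81% | 80% |

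Both forms rejected a true null about 5% of the time.

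**Limit for grip.** Grip has three time levels, so its omnibus terms have 2 df and the three-way and condition × time figures do not carry over exactly. Under compound symmetry, d = 0.9 and no control response, the three-way term has about 57% power (half the effect at 30 minutes) to 70% (full effect at both times, or at 60 only), against 66% for MIP.

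**Time levels.** With 2 groups, 2 conditions and 4 times, the stated model has 16 cells. The schedule supplies 8 for MIP, 8 for cough flow, 12 each for grip and P0.1, and 16 for tidal breathing.

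**The case against.** The strongest defence is that this is a pilot for a grant application, that the Abstract proposes comparing patients with controls under AIH and sham, and that the three-way model does that. Specific Aims does not name sham in Aim 1, so AIH versus sham within ALS is inferred. Tukey can reach that pair, and its lower power pays for family-wise error control. Two unranked tests at 0.05 would give some of that control up.

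Most of this stands, and the group comparison should stay. But a proof-of-concept claim about ALS needs one identifiable ALS result, and the plan already applies p<0.05. Tukey protects against errors over pairs that Aim 1 does not ask about. The multiplicity that does matter, MIP and MHGF, can be handled by ranking.

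Two stronger readings are tempting. A reader might infer that the planned analysis cannot test Aim 1 at all. The documents do not support this: the ALS data under both conditions are in the model, and if changes are modelled the Tukey pair is the right contrast, only undesignated and less powerful. A reader might also infer from the time levels that measurements are missing or that the analysis must fail. The list in Statistical Analysis can be read as the union of the scheduled times, with each outcome fitted at its own. That mismatch is a minor correction.

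**Conclusion.** The point holds as a cheap improvement. The plan does not designate the comparison that answers Aim 1, and the omnibus terms it does state answer different questions. For a two-level outcome at an assumed ALS effect of 0.9, naming the contrast gives 81% power. The Tukey pair on changes gives about 65%, and the three-way term 66% down to 5% as the control response rises to equal the patients'. Reading condition × time together with the three-way term does not prevent a false ALS claim: the misleading pattern occurs in about 20% to 27% of trials in the controls-only cases examined.

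All of these sizes rest on assumed effects, equal group SDs and the target numbers of completers. They show how much the choice of test matters; they do not predict this trial's results. That no Aim 1 test is named, and that four of the five schedules set out above lack one or more of the stated time levels, can be confirmed by reading alone.

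**What to change.** 1. Name as the Aim 1 test, for MIP and for MHGF, the AIH-versus-sham contrast within ALS patients at 60 minutes. Regress the 60-minute AIH-minus-sham difference on the baseline AIH-minus-sham difference, and test the intercept with the covariate left uncentred, so that it estimates the effect at equal baselines. This form had at least about equal power to difference in change in every scenario examined. Fix it before analysis. Sixty minutes is the only post-intervention time that MIP and grip share, and the plan already uses it for the caffeine comparison.
2. State whether MIP and MHGF are ranked or each tested at 0.05. Unranked, the chance of at least one false positive is 1 − 0.95² = 9.75% if the tests are independent, and at most 10%.
3. Keep the three-way ANOVA and Tukey for the ALS-versus-control comparison, and say whether they use raw values or changes. List time levels per outcome to match the schedule: MIP pre and 60; cough flow pre and 30; grip and P0.1 pre, 30 and 60; tidal breathing all four.

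The cost is a few sentences, with no new visits, patients or measurements. Other pairs become secondary. Taking error from ALS patients alone loses a few points of power if the group variances are equal (81% against 85% at d = 0.9, for the difference-in-change form).
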